7.5 Emergency Unblinding

In this single-blinded study, if the clinical condition of a participant necessitates unblinding of the participant, this will be undertaken according to a trial specific working instruction. This will be done if unblinding is thought to be relevant and likely to change clinical management.

The trial code should only be broken for valid medical or safety reasons e.g. in the case of a serious adverse event where it is necessary for the treating health care professional to know which treatment the patient is receiving before the participant can be treated.

- if unblinding of a participant is required, a formal notification of unblinding will be made by the Investigator/treating health care professional to the CI or site PI
- if the person requiring the unblinding is not the CI/PI then that health care professional will notify the Investigating team that an unblinding is required for a trial participant and an assessment to unblind the participant should be made in consultation with the clinical and research teams
- on receipt of the treatment allocation details the site PI or treating health care professional will continue to deal with the participant's medical emergency as appropriate
- the PI documents the unblinding of the participant and the reasons for doing so on the CRF/data collection tool, in the site file and medical notes. It will also be documented at the end of the trial in any final trial report and/or statistical report
- the CI/PI will notify the Sponsor in writing as soon as possible following the unblinding process detailing the necessity of unblinding.
- the CI/Sponsor will also notify the relevant authorities if required
- The written information will be disseminated to the Data Safety Monitoring Committee for review in accordance with the DMC Charter. The responsibility for which should be assigned and documented
- As the investigator is responsible for the medical care of the individual trial participant (Declaration of Helsinki 3§ and ICH 4.3) emergency unblinding is permitted without prior discussion with the Sponsor.
- SUSARs are required to be reported unblinded

7.6 Baseline data

Baseline information collected about participants will include demographic details, NHS number, prior receipt of a COVID-19 vaccine, past medical history, details of the current pregnancy including the results of antenatal screening and scans, concomitant medication and a history of vaccinations received within the last five years and in all previous pregnancies.

7.7 Trial assessments

Blood samples will be obtained from women prior to vaccination, day 28-42, day 56-84, day 84-112, day 112-140 if not delivered already, at delivery, at 4-12 weeks after delivery, and at day 364 after delivery. A cord blood sample at selected sites will be obtained at delivery and if this is not collected a blood sample can be obtained from infant. All infants will have a blood sample taken at day 42 – 84 after birth. Colostrum samples will be obtained from women participating in the breastfeeding sub-study at 72 hours after delivery where possible and breast milk at day 14 after delivery where possible.

7.8 Long term follow-up assessments

A follow up assessment of infant development is planned at 12 months after birth using the “Ages and Stages” Questionnaire. Longer term follow up assessments for infants may be considered, but will be part of separate protocol and application.

7.9 Qualitative assessments

N/A

7.10 Withdrawal criteria

In consenting to the trial, participants are consenting to trial treatments, trial follow up and data collection. However, an individual participant may stop treatment early or be stopped early for any one of the following reasons:

- Having received vaccination outside of the study after randomisation, but before vaccination by the study team
- Any change in participant’s condition that in the investigator’s opinion justifies the discontinuation of follow up
- Withdrawal of consent by the participant

As participation in the trial is entirely voluntary, the participant may choose to discontinue treatment at any time without penalties or loss of benefits to which they may be entitled. Although not obliged to give a reason for discontinuing their trial treatment/ protocol inclusion a reasonable effort should be made to establish this reason, whilst remaining fully respectful of the participant's rights.

Participants who discontinue protocol treatment, for any of the above reasons, should remain in the trial for the purpose of follow up and data analysis.

However, if the participant confirms they do not wish to participate in the scheduled follow up data collection visits, then data that has already been collected should be kept and analysed according to the ITT principle, unless the participant specifically requests otherwise.

Participants who stop the trial follow up after receiving vaccination will not be replaced. Participants who withdraw prior to vaccination may be replaced.

If there is a change in the national recommendations or a safety signal is demonstrated the trial management group would consider if the study should be prematurely stopped.

7.11 Storage and analysis of clinical (biological) samples

7.11.1 Immunology blood tests (refer to the Laboratory Analysis Plan)

Immunogenicity will be assessed by a variety of immunological assays. Collaboration with other specialist laboratories in the UK, Europe and outside of Europe for further exploratory tests may occur. This would involve the transfer of serum, plasma, PBMC and/or other study samples to these laboratories, but these would remain anonymised. The analyses and which laboratories carry these out will be specified in the laboratory analysis plan.

Subjects will be informed that there may be leftover samples of their blood (after all testing for this study is completed), and that such samples may be stored indefinitely in the Infection and Immunity Biobank at St. George's, University of London for possible future ethically approved research. Subjects will be able to decide if they will permit such future use of any leftover samples. With the participants' informed consent, any leftover cells, serum/plasma or breast milk will be frozen indefinitely for future analysis of COVID-19 and other coronaviruses related diseases or pathogen-related immune responses. If a subject elects not to permit this, all of that participant's leftover samples will be discarded at the end of the trial.

Samples that are to be stored for future research will be transferred to the Infection and Immunity Biobank at St. George's, University of London.

7.11.2 Blood sampling (refer to the Laboratory Analysis Plan)

- Blood samples will be obtained by venepuncture by appropriately trained members of the research team. If it is not possible to obtain a venous sample from the infants, capillary blood sampling is acceptable although venous blood samples are preferable.
- Samples should be labelled with the participant number (prefixed with Preg-CoV), date of sampling and study visit number.
- Cord blood volumes. The required volume of cord blood is 30mls
- Maternal blood volumes. Refer to lab manual.
- Infant blood volumes. The required volume of infant blood is up to 5ml (no more than 1% of circulating blood volume)

7.11.3 Obtaining, labelling (colostrum/breast milk)

- Colostrum and breast milk samples will be collected by hand expression into a container after the breast and hands have been thoroughly cleaned with soap and water or a hygienic wipe.
- The samples will be taken immediately following a feed and will include colostrum/breast milk from both breasts
- Samples should be labelled with the participant number, date and time of sample collection, time since last feed and study visit number.
- Samples will be sent to the laboratory at St. George's, University of London on the same day if possible or kept in the fridge overnight if this is not possible. Samples may be frozen at -20C at the participant's home if it is not possible to transfer the breast milk to the laboratory within 48 hours of collection. Samples can be transferred in a cool box with ice packs by the study team who attend the woman's home.

7.11.4 Processing and storage (colostrum/breast milk) refer to the Laboratory Analysis Plan

- The colostrum/breast milk will be centrifuged and the lipid layer removed.
- The aqueous fraction will then be transferred to cryovials and frozen at -70°C.

7.11.5 Laboratory procedures (colostrum/breast milk) refer to the Laboratory Analysis Plan

- Multiplex immunoassays and functional assays will be performed on colostrum and breast milk at St George's, University of London.

It is the responsibility of the trial site to ensure that samples are appropriately labelled in accordance with the trial procedures to comply with the 2018 Data Protection Act. Biological samples collected from participants as part of this trial will be transported, stored, accessed, and processed in accordance with national legislation relating to the use and storage of human tissue for research purposes and such

activities shall at least meet the requirements as set out in the 2004 Human Tissue Act and the 2006 Human Tissue (Scotland) Act.

See appendix 4 – Schedule of Events / Procedures

7.12 End of trial

The end of the clinical phase of the study will be the last follow up visit of the last participant enrolled in the trial. The end of the study will be after the last sample has been assayed and analysed and database has been locked.

8 TRIAL TREATMENTS

8.1 Name and description of investigational medicinal product(s)

VACCINE A - Pfizer BioNTech (BNT162b2)

BNT162b2 is a lipid nanoparticle-formulated, nucleoside-modified mRNA vaccine that encodes trimerised SARS-CoV-2 spike glycoprotein.

VACCINE B - COVID-19 Vaccine Moderna

COVID-19 Vaccine Moderna (mRNA-1273) encodes the S-2P antigen, consisting of the SARS-CoV-2 glycoprotein with a transmembrane anchor and an intact S1–S2 cleavage site. S-2P is stabilized in its prefusion conformation by two consecutive proline substitutions at amino acid positions 986 and 987, at the top of the central helix in the S2 subunit. The lipid nanoparticle capsule is composed of four lipids and formulated in a fixed ratio of mRNA and lipid.

VACCINE C - Novavax, NVX-CoV2373

Novavax, NVXCoV2373 is a nano-particle vaccine. It is constructed from the full-length wild-type (prototype Wuhan sequence) pre-fusion trimers of SARS-CoV2 spike glycoprotein. The native protein has been modified with several substitutions to limit protease cleavage and enhance thermal stability (the putative native furin cleavage site has been modified from RRAR to QQAQ and 2 proline substitutions (positions K986P and V987P) in the HR1 domain). It has also been optimised for expression in insect (*Spodoptera frugiperda*) Sf9 cells. The recombinant S-protein genes are cloned into

a baculovirus vector before being transferred into Sf9 cells. These cells then produce the protein which is extracted and purified. It is co-formulated with a saponin-based adjuvant, Matrix-M1™.

VACCINE D - AstraZeneca COVID-19 vaccine (ChAdOx1 nCoV-19) (*only for participants who have received one dose of this vaccine pre-pregnancy)

ChAdOx1 nCoV-19 is a recombinant replication-defective chimpanzee adenovirus expressing the SARS-CoV-2 spike (S) surface glycoprotein with a leading tissue plasminogen activator (TPA) signal sequence. S is a type I, trimeric, transmembrane protein located at the surface of the viral envelope, giving rise to spike shaped protrusions from the virion. The S proteins subunits are responsible for cellular receptor ACE-2 binding via the receptor-binding domain and fusion of virus and cell membranes, thereby mediating the entry of SARS-CoV-2 into the target cells. The S protein has an essential role in virus entry and determines tissue and cell tropism, as well as host range.

ChAdOx1 nCoV-19 expresses a codon-optimised coding sequence for Spike protein from the SARS-CoV-2 genome sequence accession MN908947. ChAd is a non-enveloped virus, and the glycoprotein antigen is not present in the vector but is only expressed once the genetic code within the vector enters the target cells. The vector genes are also modified to render the virus replication incompetent, and to enhance immunogenicity. Once the vector is in the nucleus, mRNA encoding the spike protein is produced that then enters the cytoplasm. This then leads to translation of the target protein which act as an intracellular antigen.

8.2 Regulatory status of the drug

VACCINE A – Pfizer BioNTech (BNT162b2)

The BNT162b2 vaccine received a conditional marketing authorisation from the European Medicines Agency on the 21st of December 2020.

VACCINE B – COVID-19 Vaccine Moderna

Approved for use under a temporary authorisation of the supply of an unlicensed vaccine; regulation 174 of the Human Medicines Regulations 2012.

VACCINE C- Novavax, NVX-CoV2373

No marketing authority or emergency use approval currently

VACCINE D - AstraZeneca COVID-19 vaccine (ChAdOx1 nCoV-19) (*only for participants who have received one dose of this vaccine pre-pregnancy)

Approved for use under a temporary authorisation of the supply of an unlicensed vaccine; regulation 174 of the Human Medicines Regulations 2012.

8.3 Product Characteristics

VACCINE A – Pfizer BioNTech (BNT162b2)

Refer to the Summary of Product Characteristics (SmPCs)

VACCINE B - Moderna

Refer to the Summary of Product Characteristics (SmPCs)

VACCINE C- Novavax, NVX-CoV2373

Refer to the Investigator Brochure

VACCINE D - AstraZeneca COVID-19 vaccine (ChAdOx1 nCoV-19) (*only for participants who have received one dose of this vaccine pre-pregnancy)

Refer to the Summary of Product Characteristics (SmPCs)

8.4 Drug storage and supply

Vaccines will be delivered to sites by Public Health England (PHE) and stored in accordance with manufacturers' recommendations.

All movements of the study vaccines will be documented in accordance with existing standard operating procedure (SOP). Vaccine accountability, storage, shipment and handling will be in accordance with relevant SOPs and forms. To allow for participants to receive the vaccine in a short time period, additional clinic locations may be used. In this instance vaccines will be transported in accordance with local SOP's and approvals as required.

VACCINE A – Pfizer BioNTech (BNT162b2)

The Pfizer BioNTech vaccine should be stored at -70°C +/- 10°C and has shelf life of 6 months. Once thawed, the vaccine may be stored for 31 days at 2-8°C. It should be used as soon as practically possible and within 6 hours of dilution.

VACCINE B – COVID-19 Vaccine Moderna

The COVID-19 Vaccine Moderna can be stored for 7 months at -25°C to -15°C. It should not be stored or transported on dry ice or below -40°C. Once thawed it should not be re-frozen and may be stored refrigerated at 2°C to 8°C protected from light for up to 30 days if not used (needle-punctured). Chemical and physical stability of an unopened vial after removal from refrigerated conditions has been demonstrated for 12 hours at 8° to 25°C. Chemical and physical in-use stability has been demonstrated for 6 hours at 2 to 25°C after first puncture. It should not be re-frozen once thawed.

VACCINE C- Novavax, NVX-CoV2373

SARS-CoV-2 rS and Matrix-M1 adjuvant should be stored at 2°C to 8°C and not frozen.

VACCINE D - AstraZeneca COVID-19 vaccine (ChAdOx1 nCOV-19) (*only for participants who have received one dose of this vaccine pre-pregnancy)

The AstraZeneca vaccine should be stored at +2°C to +8°C and has a shelf life of 6 months. The vaccine does not contain any preservative. After first opening the vial, it should be used within 6 hours when stored at room temperature (up to 30° C) or within 48 hours when stored in a refrigerator (2 to 8° C [36 to 46°F]). After this time, the vial must be discarded. The total cumulative storage time once opened must not exceed 48 hours.

8.5 Preparation and labelling of Investigational Medicinal Product

There will not be IMP labelling for this trial, products will be used as supplied by manufacturer (as for national supply) and blinding performed as per section 7.5.

8.6 Dosage schedules

VACCINE A – Pfizer BioNTech (BNT162b2)

The dose of Pfizer BioNTech COVID-19 vaccine is 30µg contained in 0.3ml of the diluted vaccine. Each pack of the Pfizer BioNTech vaccine contains 195 vials with 5 doses per vial (975 doses per pack). It is supplied with 0.9% sodium chloride diluent for injection plastic ampoules.

VACCINE B – COVID-19 Vaccine Moderna

COVID-19 Vaccine moderna (mRNA-1273) is packaged in multidose vials containing 10 doses of 0.5 mL. Vials are packaged in a carton containing a total of ten multidose vials per carton. One dose (0.5 mL) contains 0.10 mg of mRNA (embedded in lipid nanoparticles).

VACCINE C- Novavax, NVX-CoV2373

The dose of NVXCoV2373 is 5 µg recombinant spike protein with 50 µg Matrix-M1 adjuvant (0.5ml). The vaccine is supplied in 10 dose vials.

VACCINE D - AstraZeneca COVID-19 vaccine (ChAdOx1 nCOV-19) (*only for participants who have received one dose of this vaccine pre-pregnancy)

The dose of AstraZeneca COVID-19 vaccine is 0.5ml. The vaccine should be administered intramuscularly. The AstraZeneca vaccine is supplied in packs of 10 vials. Each vial contains 8 to 10 doses of vaccine, and is a colourless to slightly yellow, clear to slightly opaque liquid. Each dose is prepared by withdrawing 0.5 mL from a vial in a sterile 1 mL or equivalent syringe.

8.7 Dosage modifications

N/A

8.8 Known drug reactions and interaction with other therapies

There are currently no data on drug reactions and interactions with other therapies.

8.9 Concomitant medication

Women will not be recruited into the study if they are taking immunosuppressive medication other than inhaled or topical steroids. There are no other restrictions on medications which can be received by participants as part of participating in this study. Women should follow standard advice about the use of medication during pregnancy.

As set out by the exclusion criteria, volunteers may not enter the study if they have received: any other COVID-19 vaccine (with the exception of the sub-study participants), any investigational product within 30 days prior to enrolment or if receipt is planned during the study period, or if there is any use of immunosuppressant medication within 3 months prior to enrolment or if receipt is planned at any time during the study period (except topical steroids and short course of low dose steroids < 14 day). Concomitant medications taken at enrolment will be recorded, as will new medications taken within the 28 days after each immunisation. Subsequently only new medications taken in response to a medically attended adverse event up until 3 months post boost will be recorded. Women should follow standard advice about the use of medication during pregnancy.

8.10 Trial restrictions

Participants may take part in this study if they are already involved in research providing that, in the opinion of the Principal Investigator, this involvement will not adversely affect the conduct or outcomes of the study.

8.11 Assessment of compliance with treatment

Solicited and unsolicited AEs will be reported by the participant using an online data capturing system. These data entries will be assessed on a daily basis by the study research team. Reminder notifications to complete these daily entries will be sent to the participants. Any non-compliance with this reporting will be noted and followed up by contacting the participant to prompt them to continue with the diary entries.

8.12 Name and description of each Non-Investigational Medicinal Product (NIMP)

N/A

9 PHARMACOVIGILANCE

9.1

Term	Definition
Adverse Event (AE)	Any untoward medical occurrence in a participant to whom a medicinal product has been administered, including occurrences which are not necessarily caused by or related to that product.
Adverse Reaction (AR)	
An untoward and unintended response in a participant to an investigational medicinal product which is related to any dose administered to that participant.
 
The phrase "response to an investigational medicinal product" means that a causal relationship between a trial medication and an AE is at least a reasonable possibility, i.e. the relationship cannot be ruled out.
 
All cases judged by either the reporting medically qualified professional or the Sponsor as having a reasonable suspected causal relationship to the trial medication qualify as adverse reactions. It is important to note that this is entirely separate to the known side effects listed in the SmPC. It is specifically a temporal relationship between taking the drug, the half-life, and the time of the event or any valid alternative etiology that would explain the event.

Serious Adverse Event (SAE)	
A serious adverse event is any untoward medical occurrence that:
 
 • results in death • is life-threatening • requires inpatient hospitalisation or prolongation of existing hospitalisation • results in persistent or significant disability/incapacity • consists of a congenital anomaly or birth defect 
Other 'important medical events' may also be considered serious if they jeopardise the participant or require an intervention to prevent one of the above consequences.
 
NOTE: The term "life-threatening" in the definition of "serious" refers to an event in which the participant was at risk of death at the time of the event; it does not refer to an event which hypothetically might have caused death if it were more severe.

Serious Adverse Reaction (SAR)	An adverse event that is both serious and, in the opinion of the reporting Investigator, believed with reasonable probability to be due to one of the trial treatments, based on the information provided.
Suspected Unexpected Serious Adverse Reaction (SUSAR)	
A serious adverse reaction, the nature and severity of which is not consistent with the information about the medicinal product in question set out in the reference safety information:
 
 • in the case of a product with a marketing authorisation, this could be in the summary of product characteristics (SmPC) for that product, so long as it is being used within its licence. If it is being used off label an assessment of the SmPCs suitability will need to be undertaken. • in the case of any other investigational medicinal product, in the investigator's brochure (IB) relating to the trial in question

9.2 Operational definitions for (S)AEs

We will not require SAE reporting for women being admitted to hospital for delivery, including those women who are admitted for induction of labour and caesarean section and neither instrumental delivery nor caesarean section would be reported as an SAE although the reasons for this may be, for example, if a caesarean section took place because of a significant antepartum haemorrhage the latter would be reported as an SAE although the caesarean section would not. Whether to report complications of delivery as an SAE should be decided at the discretion of the local PI with discussion with the Sponsor and CI as necessary.

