7.4 Blinding

The study will be participant and laboratory blinded, i.e., while staff involved in study delivery will be aware of what vaccine schedule the participant is receiving, the participant themselves will remain blinded to which vaccine they receive. The "short" or "long" prime-boost interval allocation will be blinded to participant, where possible. This will be achieved in cohort 1, but in cohort 2, the pertussis-containing vaccine in the "long" prime-boost interval arm cannot be given at a COVID-19 vaccine visit (if after 32 weeks' gestation), and thus the whole cohort will be not blinded to "short" or "long" prime-boost intervals. During vaccination, the blind will be maintained by applying masking tape over the vaccine syringe. Laboratory staff will be blinded to both the randomised vaccines and the prime-boost intervals.

The timing of final unblinding of all trial participants will be after the creation of a locked analysis data set.

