9.3 Recording and reporting of SAEs, SARs AND SUSARs

Information about AEs and SAEs will be collected from the time of consent. Information about ARs, SARs and SUSARs will be collected from the time of administration of the vaccine. Information about SAEs will be collected for the duration of the study. Information about AEs will be enquired about at every study visit. AEs (apart from those which could reasonably be expected following vaccination- see section 9.2) will be recorded on the adverse event log for the period of 28 days following administration of the vaccine and medically attended adverse events which occur at any time in the study for the maternal participants will be collected. Medical attendance which is a routine part of antenatal care will not be considered an AE. Unscheduled medical attendances and events which meet the definition of an SAE should be recorded for the mother and infant.

Where a participant withdraws consent for further processing of data, this does not preclude the reporting of SARs and SUSARs which are required to continue being reported according to the protocol for regulatory purposes.

SAEs, SARs and SUSARs must be notified to the Sponsor immediately when the investigator becomes aware of the event (within 24 hours). Refer to JRESSOP0006 and ensure the completed SAE report form JRESDOC0012 is sent to the Sponsor by e-mail to [contact]. All sites will correspond directly with the Sponsor, copying the CI into the correspondence.

We will not require SAE reporting for women being admitted to hospital for delivery, including those women who are admitted for induction of labour and caesarean section and neither instrumental delivery nor caesarean section would be reported as an SAE although the reasons for this may be, for example, if a caesarean section took place because of a significant antepartum haemorrhage the latter would be reported as an SAE although the caesarean section would not. Whether to report complications of delivery as an SAE should be decided at the discretion of the local PI with discussion with the Sponsor and CI as necessary.

For each SAE and SUSAR the following information will be collected:

- full details in medical terms and case description
- event duration (start and end dates, if applicable)
- action taken
- outcome
- seriousness criteria
- causality (i.e. relatedness to trial drug / investigation), in the opinion of the investigator
- whether the event would be considered anticipated.

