9.4 Responsibilities

Principal Investigator (PI):

Checking for AEs and ARs when participants attend for treatment / follow-up.

1. Using medical judgement in assigning seriousness, causality and whether the event/reaction was using the Reference Safety Information approved for the trial.
2. Ensuring that all SAEs are recorded and reported to the sponsor within 24 hours of becoming aware of the event and provide further follow-up information as soon as available. Ensuring that SAEs are chased with Sponsor if a record of receipt is not received within 2 working days of initial reporting.
3. Ensuring that AEs and ARs are recorded and reported to the sponsor in line with the requirements of the protocol.

Chief Investigator (CI) / delegate or independent clinical reviewer:

1. Clinical oversight of the safety of patients participating in the trial, including an ongoing review of the risk / benefit.
2. Using medical judgement in assigning the SAEs seriousness, causality and whether the event was anticipated (in line with the Reference Safety Information) where it has not been possible to obtain local medical assessment.
3. Using medical judgement in assigning whether and event/reaction was anticipated or expectedness in line with the Reference Safety Information.

4. Immediate review of all SUSARs.
5. Review of specific SAEs and SARs in accordance with the trial risk assessment and protocol as detailed in the Trial Monitoring Plan.
6. Assigning Medical Dictionary for Regulatory Activities (MedDRA) or Body System coding to all SAEs and SARs.
7. Preparing the clinical sections and final sign off of the Development Safety Update Report (DSUR).

Sponsor:

1. Central data collection and verification of AEs, ARs, SAEs, SARs and SUSARs according to the trial protocol onto a database.
2. Reporting safety information to the CI, delegate or independent clinical reviewer for the ongoing assessment of the risk / benefit according to the Trial Monitoring Plan.
3. Reporting safety information to the independent oversight committees identified for the trial (Data Monitoring Committee (DMC) and / or Trial Steering Committee (TSC)) according to the Trial Monitoring Plan.
4. Expedited reporting of SUSARs to the Competent Authority (MHRA in UK) and REC within required timelines.
5. Notifying Investigators of SUSARs that occur within the trial.
6. The unblinding of a participant for the purpose of expedited SUSAR reporting [For double blind trials only].

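### Sections 9.2 and 9.3 let the local PI decide whether a delivery complication is reported as an SAE, while 9.1, 9.3 and 9.4 require every event meeting the SAE definition to be reported

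*Protocol*

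**What the plan says.** Section 9.1 defines a serious adverse event by outcome. Among the criteria is that the event "requires inpatient hospitalisation or prolongation of existing hospitalisation"; death, threat to life, lasting disability and congenital anomaly are others. Important medical events may also be judged serious. The definition makes no exception for events around delivery.

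Section 9.2, repeated in 9.3, removes admission for delivery (including for induction or caesarean section) and instrumental or caesarean delivery from SAE reporting. It separates the procedure from its cause: "if a caesarean section took place because of a significant antepartum haemorrhage the latter would be reported as an SAE". It then adds: "Whether to report complications of delivery as an SAE should be decided at the discretion of the local PI". The same sentence provides for the Sponsor and CI to be consulted, but only where thought necessary.

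Section 9.3 also contains this instruction: "Unscheduled medical attendances and events which meet the definition of an SAE should be recorded for the mother and infant". It requires SAEs to be notified to the Sponsor within 24 hours. Section 9.4 lists among the PI's duties "Ensuring that all SAEs are recorded and reported to the sponsor within 24 hours of becoming aware of the event".

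Section 7.4 says that "staff involved in study delivery will be aware of what vaccine schedule the participant is receiving"; participants and laboratory staff are the blinded parties.

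**The concern.** The exemption for the admission and the mode of delivery is sensible, because otherwise every birth in hospital would meet the hospitalisation criterion. The difficulty is the sentence after it. It covers complications of delivery in general, is not limited to those outside 9.1, and gives the PI nothing to decide by. A postpartum haemorrhage that prolongs the stay meets 9.1, yet under 9.2 its reporting is a local choice.

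SAE occurrence is a secondary endpoint for mothers and infants (3.5) and is tabulated by schedule (10.3.3). All participants who continue in the trial deliver within the collection period. SAE status also decides what happens next. The 24-hour notice to the Sponsor applies to SAEs, SARs and SUSARs (9.3), SUSARs are identified from among the SAEs (9.3), and Appendix 5 sends related SAEs to the DSMB. An analysis plan cannot restore SAEs that sites were permitted not to report, so this has to be settled in the protocol.

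**Working it through.** The document gives no SAE rate, no delivery-complication rate and no test or power for SAEs, so there is no figure to reproduce. The check is to set the rules side by side.

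| Section | Rule | Discretion? |
|---|---|---|
| 9.1 | SAE status follows from seriousness criteria | Only for other important medical events |
| 9.2, 9.3 | Admission for delivery, induction, instrumental and caesarean delivery are not SAEs | No |
| 9.2, 9.3 | Significant antepartum haemorrhage behind a caesarean is an SAE | No (example) |
| 9.2, 9.3 | Other complications of delivery | Local PI; Sponsor/CI discussion as necessary; no criteria |
| 9.3 | Events meeting the SAE definition are recorded, mother and infant | No |
| 9.3, 9.4 | SAEs are notified within 24 hours; the PI reports all of them | No |

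1. Take a delivery complication that prolongs the hospital stay. Under 9.1 it is an SAE. Under the recording instruction in 9.3 and the PI's duty in 9.4 it must be recorded and reported.
2. Under the discretion sentence the PI may decide not to report the same event as an SAE. Section 9.3 contains both rules, so the conflict exists even within that one section.
3. Site A applies 9.1 and reports the event. Site B applies the discretion sentence and does not. Each has followed a written rule.
4. Central review does not reliably correct this. Under 9.4 the CI assigns seriousness where local medical assessment could not be obtained, and the discussion in 9.2 takes place only if thought necessary.
5. Section 7.4 leaves site delivery staff aware of the schedule, so the classification may be made by someone who knows the allocation. It does not name the PI, so PI knowledge is a reasonable inference and no more.
6. Other capture limits the loss. Postpartum haemorrhage, antenatal bleeding, non-reassuring fetal status, maternal death and others are maternal AESIs, collected to 6 weeks after delivery. Stillbirth is a pregnancy outcome (3.5). Section 9.3 sets GAIA case definitions for these. The definitions standardise whether an event is a case. They do not settle whether it is serious, so the SAE count remains open to variation.

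**The case against.** The strongest reply is that the sections can be read together. Section 9.4 already asks the PI to use medical judgement in assigning seriousness, and 9.1 includes a judgement category of its own. On this reading the discretion sentence only restates that judgement, and whatever is judged serious is then recorded under 9.3. A site could read it that way. But the sentence concerns whether to report, not whether the event is serious, and nothing ties it to 9.1. If 9.2 is instead taken as an operational narrowing of 9.1, the narrowed set is undefined because no criteria are given. Either way the text needs reconciling.

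Several further points stand and limit the concern:

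- A reader might infer that reporting rests with the local PI alone. It does not: Sponsor and CI discussion is provided for, although optional, and the duties in 9.3 and 9.4 still apply. The defect is conflicting rules, not a purely discretionary regime.
- A reader might infer that delivery complications drop out of the safety data. The AESI and pregnancy-outcome capture shows otherwise, and the DSMB description in the committee roles section covers related AESIs as well as related SAEs.
- A reader might infer bias between schedules from differing site habits. Randomisation is stratified by site (7.3.1) and SAEs are summarised descriptively by schedule, so site habit is mainly noise. Differential reporting would have to come from judgement made with knowledge of the schedule, which the text permits but does not show.

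**Conclusion.** The point holds as an internal contradiction. The rule in 9.2 and 9.3 allows a complication that meets 9.1 to go unreported as an SAE, against the recording instruction in 9.3 and the PI's duty in 9.4. The same event can therefore be an SAE at one site and not at another. The exposure is to the SAE count by schedule and to the Sponsor, SUSAR and DSMB routes that depend on SAE status.

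Its size cannot be derived from the document. One might assume that 2% to 10% of the roughly 800 planned participants have a qualifying complication, giving 800 × 0.02 = 16 to 800 × 0.10 = 80 events. That rate has no source in the protocol. Treating the whole 16 to 80 as a change in the SAE count also requires every event to be reported under one rule and none under the other, which 9.3, 9.4 and the antepartum haemorrhage example contradict. It is a ceiling on an assumption and should not be read as an expected effect. The contradiction does not depend on it. The correction should be made; it does not call the design or the primary analysis into question.

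**What to change.** In both 9.2 and 9.3, keep the exemption for admission for delivery, induction, and instrumental or caesarean delivery themselves. Replace the discretion sentence with: *A complication of delivery that meets a seriousness criterion in 9.1 is recorded and reported as an SAE; discretion, with discussion with the Sponsor and CI, applies only to complications meeting none.*

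The cost is some additional SAE forms at sites, with no extra visits or assessments. Some local judgement will remain, for example on whether a delivery stay was prolonged or an event was medically important, but it will then be exercised against the protocol's own definition. The change concerns reporting only and does not touch clinical care.
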